110 **2.3. Primary Objective**

111 • To assess if there is a clinical difference in severity of ACD in participants treated with
112 anakinra compared to placebo measured by different scoring systems for ACD.

113 **2.4. Secondary Objective**

114 • To assess if there is a decrease in T_{RM} function and inflammation after treatment with
115 anakinra compared to the control group, using following methods: flow cytometry, single cell
116 RNA sequencing, immunohistochemistry, ELISA, digital spatial profiling, and qPCR.

117 **3. STUDY DESIGN**

118 **3.1. Overview**

119 This study is a prospective, two-arm, double-blinded, parallel group, randomized controlled
120 clinical trial. Participants with known nickel allergy, but with minimal signs of dermatitis, will be
121 recruited to the study until 20 has completed the study. Before enrollment, participants will be
122 screened for eligibility (blood samples (20-25 ml), Quantiferon TB Gold test, and urine test for
123 infection/pregnancy and chest x-ray to ensure that there is no evidence of infections and/or
124 malignancy). Participants will be blinded to treatment and randomly allocated into two equally
125 sized groups. At baseline (day 0) all participants will be exposed to a two-chamber patch test on
126 the lower part of their back, with one chamber containing 5 % NiCl₂ in petrolatum and one
127 chamber containing petrolatum. The patch testing will be repeated twice at the exact same skin
128 area, with an interval of 21 days between tests (day 21 and 42). One group (the control group)
129 will be treated with placebo (saline water) and the second group (the treatment group) will be
130 treated with anakinra before and during the second patch test (day 21) for six consecutive days
131 (day 20 to 25). Skin biopsies will be collected with 4 mm punch biopsies right before and 48
132 hours after the third patch test (day 42 and 44). The wounds will be closed with non-absorbable
133 sutures, and stitches will be removed after eight to ten days.

134 The study will be comprised of 12 visits in total, including screening.

135 **3.2. Outcome Measures**

136 **3.2.1. Primary Outcome Measure**

137 Photographs and clinical evaluation of the skin patch reactions will be performed on-site and
138 blinded, using the Investigators Globals Assessment (IGA) and International Contact Dermatitis
139 Research Group (ICDRG) scoring systems as instruments for classifying the severity of

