140 dermatitis. Patient reported outcomes will include Patient's Global Assessment Score (PtGA).
141 Treatment effect will be defined as a difference in score between the two groups on the scoring
142 systems used.

143 **3.2.2. Secondary Outcome Measure**

144 From each group, blood and biopsies from seven individuals will be used for single cell RNA
145 sequencing (sc-RNAseq), and/or digital spatial profiling. Skin biopsies from the remaining three
146 individuals will be used for immunohistochemistry, flowcytometry (staining with anti-CD3, anti-
147 CD8, Ki67, anti-IL-1 β) and/or qPCR (IFN- γ , IL-17A and IL-1B). Treatment effect will be defined
148 as a reduction in number of T-cells, cytokines and proliferative markers in the treatment group
149 compared to placebo.

150 **3.3. Stopping Rules and Discontinuation**

151 The Department of Dermatology and Allergy, Herlev and Gentofte Hospital can discontinue the
152 trial at any time for failure to meet expected enrolment goals, for safety or any other
153 administrative reasons. Participants and The Regional Committee on Health Research Ethics
154 will be informed in given case. The following may result in the trial being terminated

155 • Major safety concerns.
156 • Insurmountable issues with trial conduct (e.g. poor recruitment, loss of resources).

157 **3.4. Randomization and Blinding**

158 **3.4.1. Randomization**

159 The randomization will be based on a computer-generated code using random permuted blocks
160 of varying size or by sealed envelope. Access to the sequence will be confined to Region
161 Hovedstadens Pharmacy. Participants will be allocated in a 1:1 ratio to the anakinra and
162 placebo treatment arms. The sequence of treatment allocations will be concealed until
163 interventions have all been assigned and recruitment, data collection, and all other trial-related
164 assessments are complete.

165 **3.4.2. Blinding**

166 The investigators and assessors will be blinded to treatment allocation until the results of the
167 outcome measurements are recorded. Only the administering personnel will be unblinded to
168 treatment allocation and know the allocation sequence. Trial participants will also be blinded to
169 treatment allocation until the end of trial.

170 **3.5. Trial Management**

171 The trial and all clinical procedures will be conducted at The Department of Dermatology and
172 Allergy, Herlev and Gentofte Hospital. All laboratory analyses of tissue specimens will be

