309 **3.8.6. Accountability**

310 Personnel at the Department of Dermatology and Allergy, Herlev and Gentofte Hospital will
311 keep detailed records, including participant study number and name, treatment given, batch
312 number, expiry date, dose and date of administration.

313 **3.8.7. Management of blood donation and risk of infection**

314 During the study period, participants cannot donate blood as blood donors. Administration of the
315 study drug will be terminated if a participant gets an infection during the study period.

316 **3.9. Study Visit Schedule and Procedures**317 **3.9.1. Visit Schedule**

318 The visit schedule ensures proper administration of study drug, and that the relevant data and
 319 clinical procedures are collected and performed at appropriate time points.

Procedures, data collection, and drug administration	Day 0 (screening) ²	Day 2	Day 3	Day 20	Day 21	Day 22	Day 23	Day 24	Day 25	Day 42	Day 44	Day 45
Clinical diagnosis of nickel allergy	X											
Obtain informed consent	X											
Ascertain the participant is eligible for the study	X											
Collect medical history and demographic data	X											
Samples taken for routine blood and urine tests ¹		X										
Routine chest X-ray		X										
Record adverse reactions					X	X	X	X	X			
Patch testing	X				X					X		
Removal of patch test		X					X				X	
Clinical evaluation of patch test reaction		X	X	X	X	X	X	X	X	X	X	X
Clinical photography	X	X	X		X		X	X		X	X	X
Collect skin biopsies										X	X	
Collect blood samples										X	X	
Give study diary to participant	X											
Dispense either anakinra or placebo according to randomization schedule				X	X	X	X	X	X			
Start study medication: anakinra or placebo					X							
Stop study medication: anakinra or placebo									X			

320 ¹Tests will include (but will not be restricted to) full red and white blood cell count, liver function tests, creatinine, HIV, hepatitis B
 321 and C serology, urea and urine screen.

322 ²And baseline if the patient wish to participate immediately

323

324 **3.9.2. Day 0: Screening**

325 The initial visit will cover screening for eligibility and baseline assessments. For clarity, the
326 screening visit will be described here as one clinic visit. The following procedures will be carried
327 out at the screening visit:

328 • Give the participant information leaflet. Discuss the study and answer any initial

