329 questions the participant may have. Allow patient sufficient time to consider their
330 participation in the study. Discuss the study with the participant further and answer any
331 questions about the study.

332 • Obtain consent from the patient before proceeding with the study.

333 • Physical examination and confirmation of clinical diagnosis of nickel allergy.

334 • Check patient meets all eligibility criteria.

335 • Record relevant medical history and demographic data.

336 • Give study diary to participant to record self-reported outcome measures, any medical
337 problems, health service usage and adherence with study protocol.

338 • Apply first set of patch tests containing nickel.

339 **3.9.3. Day 2 and 3 visit**

340 At the day 2 visit patch tests will be removed and clinical evaluation of patch test reactions
341 including photography will be performed. Following procedures will be performed during day 2
342 and 3.

343 • Removal of patch tests.

344 • Clinical evaluation of patch test reactions.

345 • Clinical photography of skin sites.

346 If positive patch test:

347 • Take samples for full blood cell count, kidney and liver function tests, plus any others
348 that are clinically indicated. Collect sample for urine screen (sediment, protein, hCG and
349 glucose). The results of these tests will not be collected or analysed but they should be
350 checked by the clinician as per routine practice and any clinically significant findings
351 treated accordingly and recorded on the medical history if appropriate.

352 • Perform routine chest X-ray to exclude any latent infectious disease.

353 **3.9.4. Day 20 visit**

354 The purpose of the day 20 visit is to initiate the study medication treatment and randomize
355 participants into the anakinra or placebo group.

356 The following procedures will be carried out at the day 20 visit:

- 357 • Physical examination.
- 358 • Randomise participant. The participant will be randomised to receive either anakinra or
359 placebo.
- 360 • Initiate treatment 24 hours prior to the second set of patch tests with nickel chloride.

361 **3.9.5. Day 21 visit**

362 At this visit, participants will receive their second dose of study medication and a second set of
363 patch tests containing nickel chloride will be applied.

364 The following procedures will be carried out at the day 21 visit:

- 365 • Clinical evaluation of patch test reactions.

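### The day 2/3 nickel reading precedes randomisation but has no stated role in the analysis; pre-specifying it as an ANCOVA covariate could add precision at small cost

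*Combined protocol and SAP*

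**What the plan says.** Section 3.2.1 names IGA, ICDRG and PtGA, then defines the effect: "Treatment effect will be defined as a difference in score between the two groups on the scoring" systems used. No starting value, covariate or model appears there. Section 4.1 leaves the method to an analysis plan written by the investigators, to be final before the coded allocation is revealed. Section 4.2 claims 80% power for a one-point reduction with 10 per arm and gives no SD.

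The relevant design facts are these.

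- **Same site.** Section 3.1: "chamber containing petrolatum. The patch testing will be repeated twice at the exact same skin" area, with applications on days 0, 21 and 42.
- **Readings after the first challenge.** Section 3.9.3: "At the day 2 visit patch tests will be removed and clinical evaluation of patch test reactions" follows, with the evaluation repeated on day 3. The row "Clinical evaluation of patch test reaction" in the section 3.9.1 table also marks days 23, 24, 44 and 45.
- **Randomisation comes later.** Section 3.9.4: "The purpose of the day 20 visit is to initiate the study medication treatment and randomize" participants.
- **No stratification named.** Section 3.4.1: "The randomization will be based on a computer-generated code using random permuted blocks" of varying size, or sealed envelopes; reaction strength is not mentioned.
- **Entry grade.** Section 3.7.3 asks for at least ?+ on ICDRG; section 3.7.7 asks for at least +2.

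**The concern.** Participants can be expected to differ in how strongly they react to nickel. With 10 per arm and no stratification on reactivity, chance imbalance in reaction strength adds noise to the comparison. The trial already collects a pre-randomisation measure of the same response, on the same scales, at the same site and interval. The only role the protocol gives it is in screening: section 3.9.3 makes the blood, urine and X-ray checks conditional on a positive test.

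What is at stake is power. How much depends on the correlation between the first-challenge and post-treatment readings, which the documents do not give. It also depends on how far the entry threshold narrows the spread of the first reading.

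**Working it through.** **Step 1: match the readings.** Days from application to reading are 2-0 = 2 and 3-0 = 3 for the first challenge, and 23-21 = 2 and 24-21 = 3 for the second. So day 2 pairs with day 23 and day 3 with day 24. Evaluations are also scheduled on days 20 and 21, but neither is a two- or three-day reading of a fresh challenge, and day 21 follows the first dose.

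**Step 2: reproduce the plan's figure.** From section 4.2, n = 10 per arm, difference 1 point, power 80%. Two-sided alpha 0.05 is assumed. For the t test with 18 df, noncentrality = 1/(SD x sqrt(2/10)). Power is 80% when this equals 2.963, so SD = 0.755. The stated power therefore implies an SD of about 0.75; at SD 1.0 it would be 56%.

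**Step 3: continuous score, the favourable case.** ANCOVA with 17 df has noncentrality 1/(0.755 x sqrt(1-r^2) x sqrt(0.2 x (1+1/16))). The factor 1+1/16 is the expected cost of chance imbalance in the covariate.

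| r | Noncentrality | ANCOVA power | Change from 80% |
|---|---|---|---|
| 0 | 2.874 | 77.3% | -2.7 |
| 0.3 | 3.013 | 81.0% | +1.0 |
| 0.5 | 3.319 | 87.8% | +7.8 |
| 0.7 | 4.025 | 96.6% | +16.6 |

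Break-even is r = 0.26. The lost degree of freedom alone costs 0.3 points (79.7%); the rest of the loss at r = 0 comes from imbalance.

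**Step 4: graded score with an entry threshold.** Assumptions: correlated normal latent scores; a one-point latent shift; both readings rounded and clipped to 0-3; entry applied to the first reading on the scale analysed; latent SD solved in each cell so that unadjusted power is 80% among those enrolled (0.68 to 0.84); 40,000 replicates per cell. The change in power with ANCOVA, in points, is:

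| Entry rule, latent mean | r = 0 | 0.3 | 0.5 | 0.7 |
|---|---|---|---|---|
| Grade 1 or above, 2 | -2.2 | +0.2 | +4.5 | +11.0 |
| Grade 2 or above, 1.5 | -1.7 | -1.2 | +0.5 | +3.9 |
| Grade 2 or above, 2 | -2.1 | -0.8 | +1.4 | +6.0 |
| Grade 2 or above, 2.5 | -1.7 | -0.1 | +2.6 | +7.4 |

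Break-even latent r is 0.28 for grade 1 entry and 0.31 to 0.47 for grade 2 entry. A second anchoring, which fixed the observed difference at one grade with unadjusted power near 80%, gave +9.9 to +11.3 (grade 1) and +4.8 to +6.5 (grade 2) at r = 0.7. ANCOVA's null rejection rate was 4.7-5.5% across the graded scenarios checked.

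**Step 5: compare with a change score.** With grade 2 entry and latent mean 2, ANCOVA against change-score power is 77.9/66.6% at r = 0, 78.8/73.4% at 0.3, 81.5/78.9% at 0.5 and 85.9/85.8% at 0.7. In the closest cell found (latent mean 1.5, r = 0.7), change minus ANCOVA was -0.01 +/- 0.13 points. The change score was never better beyond simulation error, and it was much weaker at low correlation.

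**Step 6: can the covariate fail to vary?** With grade 2 entry on a 0-3 scale it takes only the values 2 and 3. At latent mean 1.5 and SD 0.68, 14.1% of those enrolled would be at grade 3, so the chance that all 20 are at grade 2 is about 0.859^20, or 5%. At SD 0.84 the share is 23.4% and the chance about 0.5%; at mean 2 it is below 0.1%.

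**The case against.** The strongest reply is that nothing here is wrong: an unadjusted difference between randomised arms is legitimate, and ANCOVA is an efficiency choice. That stands. A reader might infer that omitting the covariate biases the result or makes the test invalid; the documents do not support that.

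The benefit is also unproven. Day 2/3 is a first challenge and days 23/24 a re-challenge, so the correlation may be low. Under the stricter entry rule the gain at r = 0.5 is only +0.5 to +2.6 points. This stands too. A simulation with no entry threshold gives +11.9 at r = 0.7, and a reader might take that as the size of the gain. Sections 3.7.3 and 3.7.7 both state a threshold, so that is not this trial.

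A reader might infer that the analysis could be picked to favour a result, because section 4.1 does not require the plan before scores are recorded. The plan must be final before allocation is revealed, and investigators and assessors are blinded. A covariate chosen under those rules cannot be selected on the known treatment difference. The same plan can still add it.

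A reader might also infer that a baseline-adjusted rule could not mean the day 2/3 reading, since section 3.1 says "At baseline (day 0) all participants will be exposed to a two-chamber patch test on" the lower back. That is strained: the reaction to the day 0 test is naturally its day 2/3 reading. Naming the day simply removes doubt.

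Finally, the covariate depends on larger open choices, namely the primary scale, reading day and test. That is true, and it sets the order of work. It does not remove the point, because settling those choices would not by itself select this covariate.

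**Conclusion.** The point holds as a recommended, low-cost improvement in precision. On an assumed 0-3 grade, with unadjusted power at the stated 80%, ANCOVA on the matching day 2 or day 3 reading changes power by about 0 to +11 points at latent r 0.3-0.7 if entry is at grade 1 or above, and by about -1 to +7 if entry is at grade 2 or above. It may gain nothing near r = 0.3 and becomes useful from about r = 0.5. At r = 0 it costs about 2 points, or 2.7 on a continuous score.

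These figures are illustrative. SD, correlation and coding are all assumed, as are the grade that ?+ represents and the application of the threshold to the day 2/3 reading. Both thresholds are on ICDRG, so the entry-restricted ranges do not carry over directly if IGA is primary. Confidence is high that the analysis role is missing and moderate that using the reading would help.

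**What to change.** First fix the primary scale and reading day. Then add to the SAP:

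1. The between-arm comparison of the post-treatment IGA or ICDRG reading uses ANCOVA, adjusted for the same scale's reading at the same interval after the first challenge: day 2 for day 23, or day 3 for day 24. Name the covariate by its day. Do not use a change score as the primary analysis.
2. A rank-based ANCOVA is the ordinal check. In the scenarios run its power was within 0.8 points of ANCOVA.
3. If the covariate does not vary among those analysed, the analysis reverts to the unadjusted comparison.
4. The same form on days 44/45 is supporting only. Section 3.1 states "Skin biopsies will be collected with 4 mm punch biopsies right before and 48" hours after the third test, and the position of the biopsies relative to the read site is not given.
5. PtGA is adjusted only if a PtGA score is recorded before randomisation.

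Separately, reconcile the ?+ and +2 thresholds in sections 3.7.3 and 3.7.7, because they decide which range of gain applies.

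The cost is a few sentences and no new IGA or ICDRG data. The statistical price is the loss of about 2 points of power if the readings prove uncorrelated.

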213 • Presence of any condition or use of any medication which precludes the use of the study
214 drug.
215 • Allergy to any of the ingredients in the drug.

216 **3.7.5. Retention of participants**

217 To help retain participants in the study, in addition to being able to speak to the investigator,
218 participants will be able to telephone the investigator if they wish to discuss any aspect of the
219 study. For medical queries, the participant will be directed to a medical member of staff.

220 **3.7.6. Withdrawal of participants from treatment and the study**

221 Participants may be withdrawn from the trial either at their own request or at the discretion of the
222 Investigator. The participants will be made aware that this will not affect their future care.

223 Participants will be made aware (via the information sheet and consent form) that should they
224 withdraw the data collected to date may still be used in the final analysis. The reason for and
225 date of withdrawal will be recorded on the case report form. All participants who withdraw from
226 study treatment will be followed up for two weeks providing they have not withdrawn consent.

227 Participants may be withdrawn from the study for the following reasons:

228 • Withdrawal of consent.
229 • Later found to be ineligible.

230 **3.7.7. Recruitment**

231 The Department of Dermatology and Allergy, Herlev and Gentofte Hospital will recruit 20
232 participants with known nickel allergy by reviewing patient journal files and/or by advertisements
233 in newspapers, bulletin boards, social media platforms or relevant webpages. Recruitment of
234 participants will continue until 20 participants with a positive nickel allergy test (at least a +2
235 reaction on the ICDRG scoring system) have been included and completed the study. Prior to
236 enrollment participants will be screened for acute, chronic or recurring infections, malignant
237 diseases, latent or prior history of tuberculosis, granulocytopenia or conditions that increase the
238 risk of infection.

239

240 **3.7.8. Informed consent**

241 All participants will provide written informed consent. Informed consent will be obtained from
242 each participant before they undergo any study procedure. Participants will be given details of
243 the study verbally in an undisturbed environment. Prior to the visit participants will be informed

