271 done before informed consent has been obtained.

272 The investigator will inform the participant of any relevant information that becomes available
273 during the study, and will discuss with them, whether they wish to continue with the study. If
274 applicable they will be asked to sign revised consent forms.

275 If the Informed Consent Form is amended during the study, the investigator shall follow all
276 applicable regulatory requirements pertaining to approval of the amended Informed Consent
277 Form by the REC and use of the amended form (including for ongoing participants).

278 Informed consent declaration S3 from The National Committee on Health Research Ethics will
279 be used.

280

281 **3.8. Study Treatment and Regimen**

282 **3.8.1. Study Treatment**

283 At day 20 (week 3) participants will be randomized to receive either:

Anakinra 100 mg/0,67 ml

OR

284
NaCl solution 9 mg/ml

286

287 Investigator and participants will be blinded to treatment allocation. The study drug and placebo
288 will be administered by unblinded personnel. The study drug or placebo will be administered
289 subcutaneously for six consecutive days, starting on day 20.

290 At any point, if the participant experiences a life-threatening adverse reaction, treatment will be
291 terminated.

292

293 **3.8.2. Rescue Medication**

294 Use of any systemic or topical immunosuppressant/immune-modulating drugs is strongly
295 discouraged to prevent potential systemic effects not related to study intervention. Accidental
296 use of immunosuppressant or immune-modulating drugs during the study period will be
297 classified as a protocol deviation.

298 **3.8.3. Prohibited concomitant medication**

299 The administration of live virus vaccines and any form of immunosuppressive drug is not
300 permitted for all participants. Participants should continue to take medications for other
301 conditions as normal. However, if it is anticipated that the participant will need a live virus
302 vaccine during the intervention phase, they will be ineligible for entry into the study.

303 **3.8.4. Caution with other concomitant medications**

304 Concomitant use of other biological pharmaceuticals is not recommended due to an increased
305 risk of infection.

306 **3.8.5. Adherence**

307 To ensure adherence, designated personnel will administer the study drug. If a participant does
308 not adhere to the administration schedule, it will be classified as a protocol deviation.

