- 366 • Administration of the second dose of study medication right before patch testing.
- 367 • Application of second set of patch tests containing nickel chloride.
- 368 • Record adverse events.

369 **3.9.6. Day 22**

370 At this visit, participants will receive their daily dose of study medication.

371 The following procedures will be carried out at this visit:

- 372 • Administration of study medication.
- 373 • Record adverse reactions.

374 **3.9.7. Day 23**

375 This visit will comprise of patch test removal, clinical evaluation of patch test reactions and
376 administration of the daily dose of study medication.

377 The following procedures will be carried out at this visit:

378 • Administration of study medication.
379 • Record adverse reactions.
380 • Patch test removal.
381 • Clinical evaluation of patch test reactions.
382 • Clinical photography.

383 **3.9.8. Day 24**

384 At this visit participants will receive their daily dose of study medication and clinical evaluation of
385 patch test reactions and clinical photography of skin sites will also be performed.

386 The following procedures will be carried out at these visits:

387 • Administration of study medication.
388 • Record adverse events.
389 • Clinical evaluation of patch test reactions.
390 • Clinical photography.

391 **3.9.9. Day 25**

392 This visit will be the last visit where participants receive study medication.

393 The following procedures will be carried out at these visits:

394 • Administration of study medication.
395 • Record adverse events.
396 • Stop study medication after administration.

397 **3.9.6. Day 42, 44 and 45 visits**

398 The remaining visits are at day 42, 44, 45.

399 At day 42, the following procedures will be carried out:

400 • Clinical evaluation of patch test reactions.
401 • Application of third set of patch tests containing nickel chloride.
402 • Collection of blood samples and skin biopsies for analysis.

403 • Clinical photography.

404 At day 44, the following procedures will be carried out:

405 • Removal of patch tests 48 hours after application.

406 • Clinical evaluation of patch test reactions.

407 • Clinical photography.

408 • Collection of blood samples and skin biopsies for analysis and closure of wounds.

409 • Collect the completed study diary and record self-reported outcome measures, medical

410 problems, health service usage and adherence with study protocol.

411 At day 45, the following procedures will be carried out:

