- 453 • Inpatient hospitalisation or prolongation of existing hospitalisation
- 454 • Persistent or significant disability / incapacity
- 455 • A congenital anomaly or birth defect in the offspring of a participant
- 456 • Other medical events may be considered to be a SAE if they require medical or surgical
457 intervention to prevent one of the outcomes listed in this definition.

458 All adverse events will be assessed for seriousness, expectedness and causality (not related,
459 possibly related, probably related or definitely related). An adverse event whose causal
460 relationship to the study drug is assessed by the Chief Investigator as "possible", "probable", or

461 “definite” is an Adverse Reaction (AR). If the AR is classed as serious then it is a Serious
462 Adverse Reaction (SAR). A distinction is drawn between serious and severe AEs. Severity is a
463 measure of intensity whereas seriousness is defined using the criteria above. Hence, a severe
464 AE need not necessarily be serious. All adverse events will be recorded and closely monitored
465 until resolution, stabilisation, or until it has been shown that the study medication or treatment is
466 not the cause. The summary product characteristics for Kineret® will be used as a reference
467 document to assess if an AE or SAE is expected or unexpected.

468 **5.2. Causality**

469 **Not related or unlikely:** a clinical event including laboratory test abnormality with temporal
470 relationship to trial treatment administration which makes a causal relationship incompatible or
471 for which other drugs, chemicals or disease provide a plausible explanation. This will be
472 counted as “unrelated” for notification purposes.

473 **Possible:** a clinical event, including laboratory test abnormality, with temporal relationship to
474 trial treatment administration which makes a causal relationship a reasonable possibility, but
475 which could also be explained by other drugs, chemicals or concurrent disease. This will be
476 counted as “related” for notification purposes.

477 **Probable:** a clinical event, including laboratory test abnormality, with temporal relationship to
478 trial treatment administration which makes a causal relationship a reasonable possibility, and is
479 unlikely to be due to other drugs, chemicals or concurrent disease. This will be counted as
480 “related” for notification purposes.

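### The two-week follow-up after stopping study treatment (section 3.7.6) ends on day 34 to 39, so it does not secure the day 42–45 readings or either biopsy, and it is not reconciled with section 3.6.1

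*Combined protocol and SAP*

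**What the plan says.** The rule is in section 3.7.6. Its sentence opens at the end of "date of withdrawal will be recorded on the case report form. All participants who withdraw from" and continues "study treatment will be followed up for two weeks providing they have not withdrawn consent". The document gives no other length of follow-up after a treatment stop. The same section lists two reasons for leaving the study (withdrawn consent and ineligibility discovered later) and also allows withdrawal at the investigator's discretion.

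Section 3.8.1 has the drug or placebo given "subcutaneously for six consecutive days, starting on day 20". Section 3.1 confirms the dosing window and times the tissue: "day 20 to 25). Skin biopsies will be collected with 4 mm punch biopsies right before and 48" and then "hours after the third patch test (day 42 and 44). The wounds will be closed with non-absorbable". For the period after dosing, the section on the day 42, 44 and 45 visits says "The remaining visits are at day 42, 44, 45". The schedule in section 3.9.1 has no column between day 25 and day 42.

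Two provisions end dosing. Section 3.8.7 says that administration of the "study drug will be terminated if a participant gets an infection during the study period", and section 3.8.1 ends treatment after a life-threatening reaction. Neither says what follow-up then applies.

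Section 3.6.1 places every participant in the study for two months with 12 visits. Section 4.1 makes the analysis per protocol. Sections 3.1 and 3.7.7 continue recruitment until 20 people have completed.

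**The concern.** The follow-up attached to a treatment stop looks too short to reach the assessments that matter later. All the tissue and the whole third challenge fall on days 42 to 45. The secondary objective, T_RM function and inflammation, rests on that material.

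If a participant who stops dosing but is willing to continue is released after two weeks, those data are never collected, and no later decision about the analysis can recover them. A stop can follow from infection, which the protocol lists as an anakinra effect, so the people lost need not be a random subset of the arm. The day 42–45 comparison could then set a selected anakinra group against a less selected placebo group.

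**Working it through.** The check is date arithmetic.

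Inputs:
- Dosing days: 20 to 25 (sections 3.1 and 3.8.1)
- Follow-up after a stop: two weeks = 14 days (section 3.7.6)
- Scheduled visits after day 25: days 42, 44 and 45 (section 3.9.1 and the section on those visits)

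End of follow-up = stop day + 14. Shortfall = 42 − end of follow-up.

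| Stop day | Follow-up ends | Days short of day 42 |
|---|---|---|
| 20 | 34 | 8 |
| 21 | 35 | 7 |
| 22 | 36 | 6 |
| 23 | 37 | 5 |
| 24 | 38 | 4 |
| 25 | 39 | 3 |

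Counting from the last dose received instead of the stop day does not move any end date past day 39. Turned round, a 14-day window would have to start no earlier than day 42 − 14 = 28 to reach day 42, day 30 to reach day 44, and day 31 to reach day 45. All three are after the last dosing day. Reaching day 45 needs 45 − 25 = 20 to 45 − 20 = 25 days of follow-up.

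What falls inside the window: second-challenge readings up to day 25, for any stop day. After day 25 the window contains no scheduled assessment.

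What falls outside it: the day 42, 44 and 45 readings, and the blood samples and biopsies on days 42 and 44.

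Scale: one participant is 1/10 = 10% of an arm. Section 3.2.2 divides each arm's tissue between seven and three people by assay, so one person is 1/7 = 14% or 1/3 = 33% of an assay subset.

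The sample size in section 4.2 cannot be reproduced, because no standard deviation is stated, and this point does not depend on it. As an illustration only: 10 per arm gives 80% power for a one-point difference (two-sided 5% t test) if the standard deviation is about 0.75. With that assumed value, power is 78% at 9 v 10, 75% at 9 v 9 and 69% at 8 v 8. Losing one or two people costs modest power; selection is the greater worry.

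**The case against.** The strongest reply is that section 3.7.6 sets a follow-up period and does not forbid later visits. A reader might infer that every participant who stops treatment must lose all the late data. The documents do not support that. Section 3.6.1 has everyone in the study for two months, and stopping treatment is not among the listed reasons for leaving the study, so two weeks could be meant as a minimum. This stands as far as it goes. But no section says that these participants attend days 42 to 45, and the specific rule is the shorter one. If the longer stay is intended, sections 3.6.1 and 3.7.6 still have to be reconciled.

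A reader might also take the loss to be certainly related to arm. That goes too far. Section 3.7.6 speaks of participants who withdraw from treatment, while sections 3.8.1 and 3.8.7 speak of treatment being terminated, and nothing expressly joins them. The 1–10% frequency for serious infections in section 1.2.4 carries no exposure period or placebo comparison, so it cannot be turned into an expected number of stops over six days. What remains is that no other follow-up rule covers these terminations.

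Nor is there a clear conflict with section 5.1. It says "AE need not necessarily be serious. All adverse events will be recorded and closely monitored" until they resolve, stabilise or are shown not to be due to treatment, and that can run alongside a two-week general follow-up.

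Finally, the per-protocol analysis would probably exclude these participants anyway, since missed dosing is a protocol deviation under section 3.8.5, and recruitment until 20 complete would replace them. This limits the effect on the planned result. It does not remove the selection, because a replacement restores the count but not the comparison between the groups as randomised.

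**Conclusion.** The concern holds in a limited form. For a stop on any dosing day, the two weeks run out on day 34 to 39, which is 3 to 8 days before the next scheduled visit. Read as written, section 3.7.6 does not secure the third-challenge readings or either biopsy for participants who stop treatment, and it is not reconciled with section 3.6.1.

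The loss is confined to the third challenge and the day 42 and 44 samples. It would be wrong to say that no analysis of all randomised participants is possible: second-challenge readings can be in hand, and the primary outcome in section 3.2.1 names no time point.

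That the loss could be related to arm rests on two things: that the two-week rule, being the only one given, is applied to terminations under sections 3.8.1 and 3.8.7, and that infection is more frequent on anakinra. The number affected is unknown.

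**What to change.** Reconcile section 3.7.6 with section 3.6.1 by replacing the two-week limit with wording such as: *Stopping study treatment is not leaving the study. Participants who stop and have not withdrawn consent are asked to attend the scheduled visits to day 45 for outcome assessment. Whether the patch challenge and biopsies are done at those visits is for the investigator to decide.* State that this also covers dosing terminated under sections 3.8.1 and 3.8.7. The listed reasons for leaving the study, including later ineligibility, need not change for this purpose.

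On the case report form, record stopping treatment and leaving the study as separate events, each with its date and reason.

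In section 4.1, add an analysis of all randomised participants with available data, reported beside the per-protocol analysis. Without it, the extra data would probably go unused.

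The cost is protocol wording, a case report form field and one further analysis; the visits are already in the schedule. The downside is that a few participants with incomplete dosing are assessed on days 42 to 45.
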